8.1 Methods for handling missing values

As part of the trial management process missing data is closely managed with the intention of minimising the amount of missing data to the lowest level possible. Particular attention will be placed upon primary and secondary end point data.

SCTRU will regularly review the data for compliance with the protocol, and for inconsistent or missing data. Should any missing data or data anomalies be found, queries will be sent to the site for resolution. Sites are expected to respond to queries within a timeous manner.

All missing data is queried with sites and where the data cannot be sources an explanation is required and quality assurance procedures are applied to validate the quality and completeness of the data before any analysis is carried out.

Once the data has been declared as ready for analysis a missing value analysis will be carried out. This will describe the pattern of missing data, identify where the missing data are located and how extensive it is, identify pairs of variables which have missing values in multiple cases and assess if data is missing randomly.

Means, standard deviations, covariates and correlations for different missing value methods (listwise, pairwise, regression and expectation-maximisation) will be produced.

Where missing data is above an acceptable level of 10% for any primary or secondary outcome data or explanatory covariates multiple imputation will be considered.

9 Reference list

1. Eisenhauer EA, *et al.* New response evaluation criteria in solid tumours: Revised RECIST guideline (version 1.1). *Eur J Cancer* **2009**;45:228-47.
2. National Cancer Institute. Cancer Therapy Evaluation Programme. Common Terminology Criteria for Adverse Events v4.0. Available at http://ctep.cancer.gov/protocolDevelopment/electronic_applications/ctc.htm
4. Vollset, S. E. 'Confidence intervals for a binomial proportion', *Statistics in Medicine*, **12**, 809–824 (1993).
5. Koyama, Tatsuki, and Heidi Chen. "Proper inference from Simon's two-stage designs." *Statistics in medicine* vol. 27,16 (2008): 3145-54. Available at <https://onlinelibrary.wiley.com/doi/10.1002/sim.3123>.

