3.1 Interim Analysis

An interim analysis will be performed after thirteen patients have been recruited (recruitment will only be suspended for the purposes of conducting the interim analysis if no improvement in the Mayo Classification has been seen in any patients at the point where the thirteenth patient is recruited). The contents of this report are outlined in this section. Further details regarding the composition of the relevant patient populations are provided in [Section 4](#).

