3.1.2 Early stopping rules

Stopping for reasons of futility: if zero evaluable patients have shown an improvement in disease, from screening to week 9, the trial will be stopped for futility. The rule for futility is specified in ([Section 1.1](#)) with further details set out in the efficiency analysis section ([Section 7.6.1](#)).

Stopping for reasons of patient safety: completion rates for patient safety data in the ITT population (see [Section 4.2](#) for population definition) to assess whether the early stopping rules have been violated will be prioritised for review by the DMC. Should data completion be adequate to assess the early stopping rules (i.e., complete data for thirteen patients), each rule will be assessed. If any rules are violated the trial will be stopped for reasons of patient safety. These rules are specified in [Section 5.2](#) with further details set out in the safety analysis section ([Sections 7.5.1, 7.5.2 and 7.5.3](#)).

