3.1.4 Efficacy

Analyses relating to efficacy endpoints will be carried out on the evaluable population (see [Section 4.3](#) for population definition); these analyses will be further specified in [Section 6Error! Reference source not found.](#) with further details set out in the Efficacy analysis section ([Section 7.67.6.1](#)). All endpoints will also be calculated for the ITT population to ensure that the conclusions drawn are the same in the context of patient discontinuation/compliance; this will require a change in denominator where percentages are calculated ([Section 6.1Error! Reference source not found.](#)).

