3.2 Final Analysis

The final analysis will be performed after all data for 20 evaluable patients has been obtained. The analyses performed and the data presented is as described in [Section 3.1](#) for the interim report.

If analysis findings with regards to efficacy endpoints for the evaluable population and the ITT population conflict (see [Section 3.1.4](#)), the DMC will discuss and advise with regards to the interpretation of these results.

In addition, 80% two-sided confidence intervals (to correspond to the 10% 1-sided sample size calculation) for the proportions relevant to the efficacy endpoints will be calculated using the approach in Koyama and Chen⁵ (again using both the evaluable and ITT populations as alternative contexts).

4 Populations and sample size

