4.1 Sample Size Calculations and recruitment schedule

The aim is to recruit 20 patients over a 24 month period. A Simon two stage minimax design to distinguish a <5% from a >25% improvement in the Mayo classification requires 20 evaluable patients (90% power, 10% 1-sided).

Thirteen patients would be recruited in the first stage. If no patients demonstrate an improvement in their Mayo classification between screening and week 9, accrual to the clinical trial would stop (see [Section 3.1.2](#)). If one or more patients demonstrate an improvement in the Mayo classification between screening and week 9, a further seven patients would be recruited (to the final total of 20 evaluable patients). In order for the clinical trial to be considered a success, at least three evaluable patients should demonstrate an improvement in disease or treatment between screening and week 9 (see [Section 7.6.1](#)).

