4.3 Evaluable Population

The evaluable population includes all patients in the ITT population who have received at least one dose of the study drug (including any patients who were enrolled in error, received study drug and were subsequently found to be ineligible).

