7.6.1 Primary endpoints

NB. For all primary endpoint assessments, if a patient does not have a week 9 scan, then their week 3 scan (if available) should be used instead.

7.6.1.1 For patients presenting at screening with a Mayo Classification of Level 1 or above

- The number and percentage of patients with an improvement in the Mayo Classification between screening and week 9 (see [Section 6.1](#) for Mayo classification system).
- The number and percentage of patients with no change in the Mayo Classification between screening and week 9 (see [Section 6.1](#) for Mayo classification system).
- The number and percentage of patients with deterioration in the Mayo Classification between screening and week 9 (see [Section 6.1](#) for Mayo classification system).

7.6.1.2 For patients presenting at screening with a Mayo Classification of Level 0

- The number and percentage of patients demonstrating improvement in status, i.e.:

- For patients presenting with right renal vein tumour thrombus: a change of tumour thrombus from main renal vein to branches of the renal vein between screening and week 9.
- For patients presenting with left renal vein tumour thrombus: a change of tumour thrombus from the main renal vein between screening and week 9 as follows:
 - If the patient is lateral to the gonadal vein at screening, a change from the main renal vein into the segmental veins
 - If the patient is medial to the gonadal vein at screening, a change from the main renal vein medial to the gonadal vein to the renal vein lateral to the gonadal vein
- The number and percentage of patients with no change in tumour thrombus status (i.e., tumour still present in the main renal vein and medial to the gonadal vein (on left side)) between screening and week 9.
- The number and percentage of patients demonstrating an extension of the thrombus into the inferior vena cava between screening and week 9.

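### Does the multiple-imputation sentence in SAP 8.1 leave the 0-of-13 and at-least-3-of-20 decisions undefined when a treated patient has no usable scan?

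*SAP*

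**What the plan says.** The rules that decide the trial are counts.

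- Interim futility (SAP 3.1.2): "if zero evaluable patients have shown an improvement in disease, from screening to week 9, the trial will be stopped for futility".
- Success (SAP 4.1): "at least three evaluable patients should demonstrate an improvement in disease or treatment between screening and week 9".
- Denominator (SAP 4.3): "The evaluable population includes all patients in the ITT population who have received at least one dose of the study drug". A scan is not required. Protocol 5.3 replaces only patients who never start treatment.
- Missing week 9 scan (SAP 7.6.1): "if a patient does not have a week 9 scan, then their week 3 scan (if available) should be used instead". The result categories that follow are improvement, no change, and deterioration or extension into the vena cava.
- ITT version (SAP 3.1.4): "this will require a change in denominator where percentages are calculated".
- Interval (SAP 3.2): "80% two-sided confidence intervals (to correspond to the 10% 1-sided sample size calculation) for the proportions relevant to the efficacy endpoints", by a method made for Simon two-stage data.

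SAP 8.1 then adds a general passage on missing data: where these are "above an acceptable level of 10% for any primary or secondary outcome data or explanatory covariates multiple imputation will be considered". Primary outcome data are thus named. No model, number of imputations or combining rule is given. SAP section 7, which presents itself as the full working specification of the analysis, contains no imputation.

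**The concern.** Taken literally, SAP 8.1 lets the primary outcome be imputed, while the two decision rules and the two-stage interval each need a single whole number. Multiple imputation produces one count per completed dataset, and the SAP does not say how to turn several counts into one verdict. SAP 7.6.1 stops at the week 3 fallback and has no category for a patient with no scan at all.

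One improvement decides the interim and three decide the trial. Near those limits the same data could pass in some completed datasets and fail in others. The trial is open label with a single arm, so whether to impute might be settled with the observed count already known. If so, the verdict would rest on a choice made after the data were seen.

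**Working it through.** **Inputs.** From SAP 4.1: rates of 5% and 25%, 13 then 7 patients, stop at 0 of 13, success at 3 or more of 20, 90% power, 10% one-sided. The number of treated patients with no usable scan is not in the documents; 0 to 4 of 20 is assumed.

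**The plan's own figure.** Success means at least 3 of 20, less the paths that stopped at 0 of 13:

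P(success) = P(Bin(20, p) ≥ 3) − (1 − p)^13 × P(Bin(7, p) ≥ 3)

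- p = 0.05: 0.0755 − 0.5133 × 0.0038 = 0.0736
- p = 0.25: 0.9087 − 0.0238 × 0.2436 = 0.9030

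A full minimax search returns the same design, so it reproduces.

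**Patients without a scan kept in the 20 and adding zero** (averaged over how they fall between the stages for 1 to 3; range over the possible splits for 4):

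| No usable scan | Type I error (5%) | Power (25%) |
|---|---|---|
| 0 | 7.4% | 90.3% |
| 1 | 6.5% | 88.2% |
| 2 | 5.7% | 85.8% |
| 3 | 4.9% | 82.9% |
| 4 | 4.1% to 4.3% | 78.5% to 80.3% |

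The type I error never rises above its complete-data value.

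**When SAP 8.1 is triggered.** 2/20 = 10%, which is not above the limit; 3/20 = 15% is. At the interim, 1/13 = 7.7% is not and 2/13 = 15.4% is. These patients must lack both the week 9 and the week 3 scan.

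**What imputation could do at the final analysis.** With three or more observed improvements it cannot change the result. With 2 of 17 improved and 3 missing:

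- Imputing at the observed rate: mean count 20 × 2/17 = 2.35; P(at least one of three improves) = 1 − (15/17)^3 = 31%.
- Drawing the rate from its posterior (Jeffreys or uniform prior): 35% or 39%.

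So 61% to 69% of completed datasets still fail, and the mean count is below 3. At the observed rate, the pooled count reaches 3 only when 20 × 2/(20 − m) ≥ 3, that is at m = 7 missing. With posterior draws, a majority of datasets passes only from 5 missing.

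**At the interim.** With 0 of 11 improved and 2 missing, imputing at the observed rate adds nothing. Posterior draws show at least one improvement in 1 − (11.5 × 12.5)/(12 × 13) = 8% of datasets (Jeffreys) or 1 − (12 × 13)/(13 × 14) = 14% (uniform). That share comes wholly from the prior.

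**How often the final case could arise.** With exactly 3 missing, a trial that continues and ends at exactly 2 observed improvements has probability 14.0% at a true rate of 5%. If each patient had an assumed 5% chance of having neither scan, P(at least 3 of 20) = 7.5%, and 0.075 × 0.140 is about 1% of null trials. At an assumed 2% chance, 0.7% × 14.0% is about 0.1%. Both products are rough, because the 14.0% applies to exactly 3 missing.

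**The case for a change.** The best case for a change is that SAP 8.1 names primary outcome data with no exception, and a pre-specified decision should not carry an option that could alter it. Section 7 claims completeness yet has no row for a patient who cannot be assessed. One sentence in each place would cost nothing, and the ITT analysis already follows the same convention, since untreated patients enter the denominator only. If two observed improvements with three missing were ever called a success, the type I error would exceed the 10% design level.

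The textual part stands: the convention is implied, not written. The rest is weaker.

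- The rules count patients who have shown or demonstrated improvement. A patient without a scan has shown none, so an analyst following sections 3, 4 and 7 reaches one answer without choosing anything.
- Imputation is only to be considered, in general wording that is not tied to either decision. SAP 8.1 places this work after the data are declared ready for analysis and does not mention the interim.
- The inflated error needs a verdict that most completed datasets contradict. It is not an upper limit either: one observed improvement with three missing also reaches three in 1% to 4% of completed datasets. It describes no rule in the plan.
- Losing both scans should be uncommon. Protocol 5.2.4 schedules a week 3 MRI for every patient. Protocol 5.3 keeps discontinued patients under efficacy follow-up unless they are lost, die or withdraw consent. Protocol 4.2 asks for a CT after removal for intolerable toxicity. SAP 8.1 has missing items queried with sites.

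Patients not yet at week 9 at the interim are a separate matter. The trigger is recruitment ("An interim analysis will be performed after thirteen patients have been recruited"), so those patients are pending, not missing.

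**Conclusion.** No change is needed. The plan already gives one sound decision: a treated patient with no usable scan stays in the denominator and does not count as improved, so the 0-of-13 and 3-of-20 rules and the two-stage interval all have a whole-number count to work from. Type I error is then at most 7.4%, within the 10% design level. The price is power, at 88.2%, 85.8% or 82.9% with 1, 2 or 3 such patients. That loss follows from defining evaluable by one dose and is the usual conservative trade-off.

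The imputation sentence is loose general wording. It could bear on the final verdict only with at least 3 of 20 patients lacking both scans and fewer than three observed improvements, and even at 2 of 17 only 31% to 39% of completed datasets would reach three. These sizes rest on assumed numbers of missing scans and on a simple imputation model, because the documents give neither. If the SAP were being revised for other reasons, stating that any imputation of the primary outcome is a sensitivity analysis would be harmless tidying.
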